### **C. Study Day**

Day 1 is defined as the date of treatment. Study day is calculated relative to the date of Day 1. The day before Day 1 is Day -1.

- If an event occurs after Day 1, Study Day = Event Date – Date of Day 1 +1;
- If an event occurs prior to Day 1, Study Day = Event date – Date of Day 1.

### **D. Missing Data**

Unless stated below, no imputation will be performed on missing safety and efficacy data. Missing data are simply noted as missing or “-” in tables and listings. If a baseline value is missing, change from baseline will not be calculated.

*Missing or Partial Heart Failure Diagnosis Date.* Partial heart failure diagnosis dates will be imputed in order to calculate the disease duration.

- A completely missing diagnosis date will not be imputed.

- A heart failure diagnosis date missing the month and day will be imputed as Jan 1st of the year.
- A heart failure diagnosis date missing the day will be imputed as the 1st of the month.

*Missing Dates in Adverse Events form and Concomitant Medications form.* Every effort will be made to avoid missing/partial dates in on-study data including AE and medication start and stop dates. Dates from these forms will be reported in listings as collected.

AEs that cannot be definitely determined as occurring prior to study IP administration will be counted as treatment-emergent adverse events (TEAEs) unless either the partial start date or a partial or complete end date documents the AE as occurring prior to treatment. Partial dates of AEs will be imputed as follows:

- Completely missing start date will not be imputed, and the event will be considered treatment-emergent unless the answer to “Did the event occur during or after study drug infusion?” is “No, event is not treatment emergent” on the Adverse Events CRF form.
- Start date missing both the month and day will be imputed as:
  - The IP administration date if the year of the start date is the same as that of the IP administration date.
  - Otherwise, Jan 1st of the year of the start date will be used.
- Start date missing the day will be imputed as:
  - The IP administration date if the year and month of the start date are the same as that of the IP administration date.
  - Otherwise, the 1st day of the month of the start date will be used.
- Partial or missing AE stop dates will not be imputed.

If the answer to “Did the event occur during or after study drug infusion?” is “Yes, event is treatment emergent” on the Adverse Events CRF form, the event will be considered treatment-emergent.

Partial dates entered on the Concomitant Medications (CM) form will be imputed as follows, for the purposes of determining whether the record is a prior or concomitant medication:

- Completely missing stop date will not be imputed. Medications will be considered as concomitant.
- Stop date missing both the month and day will be imputed as Dec 31st of the year of the stop date.
- Stop date missing the day will be imputed as the last date of the month of the stop date.

After imputation, the imputed date will be compared against the date of death, if available. If the planned imputed date is later than the date of death, the date of death will be used as the imputed date instead. If there is no date of death in the EDC for a subject and the planned imputed date is later than the End of Study date, then the End of Study date will be used for the stop date.

## **E. Multiple Study Centers**

No adjustment for study center is planned. Data from all investigational sites will be pooled in the analyses.

## **F. Covariate Adjustment in Primary Analysis**

No covariate adjustments are planned.

## **G. Sample Size Reassessment**

Not Applicable.

## **H. Interim Analyses**

No formal interim analyses are planned. Handling of the safety results and the data reports for DRC are described in the DRC Charter. Pharmacokinetic parameters will be calculated using available JK07 concentrations and scheduled sampling times.

## **I. Test Sizes**

Not Applicable.

## **J. Multiple Comparisons**

Not Applicable.

## **K. Analysis Populations**

Five (5) analysis populations will be defined for use with various analyses:

- Safety Evaluation Population: subjects who are randomized and have a dose of IP (either JK07 or placebo) administered. Subjects will be analyzed according to the treatment they received.

- Dose-Limiting Adverse Event (DLAE) Evaluation Population: all subjects in the safety population who have a dose of IP (either JK07 or placebo) administered and have completed the 15-day DLAE follow-up period (Day 1 to Day 15). Subjects will be analyzed according to the treatment they received.
- PK Evaluation Population: subjects who have a dose of IP (either JK07 or placebo) administered and have at least one quantifiable IP plasma concentration collected after dose IP administration, with no major protocol deviations which are considered to affect the PK results. This population will be used for the PK concentration data summaries and listings.
- PK Parameter Population: subjects from PK Evaluation Population who had at least 1 PK parameter of JK07 available. Subjects will be excluded from the PK analysis if they have too few serum concentration data points to allow accurate assessment of PK parameters. This population will be used for the PK parameter data summaries and listings.
- Exploratory PD/biomarker Evaluation Population: The PD population will include all randomized subjects who have a dose of IP (either JK07 or placebo) administered and have at least one post-baseline exploratory PD endpoint collected post-dose without any major protocol deviations which are considered to affect the PD results. The PD population will be used for the analyses/summaries of PD/biomarker endpoints. Subjects will be analyzed according to the treatment they received.

Criteria for major protocol deviations excluding subjects from the PK or PD evaluation population will be determined based on a blinded review of the data prior to the unblinding of the study, as defined in the Clinical Monitoring Plan. Subjects with protocol deviations affecting PK or PD results will be determined prior to the database lock.

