## 6.3 Randomization and Blinding

All subjects other than sentinel subjects will be centrally assigned to randomized study treatment using an Interactive Voice/Web Response System (IVRS/IWRS). Before the study is initiated, the telephone number and call-in directions for the IVRS and/or the log in information & directions for the IWRS will be provided to each study center.

Subjects will be randomized to study treatment via stratified randomization. Separate randomization schedules will be used within each cohort (randomly permuted blocks within strata).

Blind Break (IVRS/IWRS)	The IVRS/IWRS will be programmed with blind-breaking instructions. In case of an emergency, the Investigator has the sole responsibility for determining if unblinding of a subject's treatment assignment is warranted. Subject safety must always be the first consideration in making such a determination. If the Investigator decides that unblinding is warranted, the Investigator should make every effort to contact the Trial Management Associate and Sponsor prior to unblinding a subject's treatment assignment unless this could delay emergency treatment of the subject. Under no circumstances should there be any delay in emergency treatment of a subject. If a subject's treatment assignment is unblinded, the Sponsor must be notified within 24 hours after breaking the blind. The date and reason that the blind was broken must be recorded in the source documentation and case report form (eCRF), as applicable.
Blinded FIH which may require unblinding subject/cohort	After each dose group, the DRC will determine the dosing regimen(s) for the next cohort. This decision will generally be made without breaking the randomization code. If judged necessary by the DRC, an individual or the complete cohort may be unblinded during evaluation of the study data. Before unblinding, a decision should be made about the action to be taken based on the revealed treatment allocation. The rationale for unblinding, etc., will be documented in meeting minutes.

Sentinel Subject	Each cohort at a new dose level higher than those previously tested shall have a single unblinded sentinel subject who will receive active treatment.
Unblinding by cohort	Thirty days following the decision by the DRC to dose escalate to a new dose level, unblinding of the previous cohort is permitted.

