**Table 11 Analysis Sets**

Analysis Set	Description
Safety Evaluation Population	All subjects randomly assigned to the IP and who take at least 1 dose of IP. Subjects will be analyzed according to the treatment they received.
Dose-limiting Adverse Event (DLAE) Evaluation Population	All subjects who received at least 1 dose of IP and completed the 15-day DLAE follow-up period.
Pharmacokinetic (PK) Evaluation Population	All subjects who received at least 1 dose of IP and have at least 1 quantifiable IP plasma concentration collected postdose without important protocol deviations/violations or events thought to significantly affect the PK results.
Exploratory Pharmacodynamic (PD)/Biomarker Evaluation Population	All subjects who take at least 1 dose of IP and have at least 1 exploratory PD variable or biomarker endpoint collected postdose without important protocol deviations/violations or events thought to significantly affect the PD results.

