### **D. Treatment Randomization**

Double blind randomization with placebo control is employed in this study to minimize bias. All subjects other than sentinel subjects will be centrally assigned to randomized study treatment using an Interactive Web Response System (IWRS). Before the study is initiated, the log in information & directions for the IWRS will be provided to each study center. Study treatment will be administered by the site.

For those subjects other than sentinel subjects, prior to randomization each subject will be assigned a unique number (randomization number) in ascending numerical order at each study center. The randomization number encodes the subject's assignment to either JK07 or placebo, according to the randomization schedule generated prior to the study by the Randomization Biostatistician at IQVIA Biotech. Each subject will be dispensed blinded study treatment, labeled with his/her unique randomization number on Day 1 of the study.

The details of randomization and unblinding plan and randomization schedule are documented separately.

Subjects will be randomized to study treatment at cohort level. After a sentinel patient is enrolled, each cohort will randomize 4 subjects in a 3:1 ratio to JK07 vs. Placebo. Subject stratification is not required.

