## **B. Disposition**

The summary table of subject disposition will include all screened subjects and display the following by treatment (if applicable):

- Number of subjects who screened
- Number and percentage of subjects who failed screening with the failed inclusion/exclusion criteria as the reason of screen failure
- Number of randomized subjects
- Number and percentage of randomization failures, using the number of randomized subjects as denominator for the percentages. Randomization failure subjects are those that passed initial screening assessments and were randomized into the trial but failed out on Day 1 due to any Day 1 labs/assessments making them ineligible (e.g., they had become pregnant, lab values were unacceptable per exclusion criteria, any morning test results were exclusionary).

Subjects who discontinued the study with discontinuation reason = “Randomization Failure” on the Study Discontinuation Form will be counted as randomization failures in the summary.

- Number and percentage of subjects in each analysis population, using the number of randomized subjects as denominator.
- Number and subjects discharged later than Day 3.
- Study completion status (completed or permanently discontinued). List the number and percentage of subjects for each reason of discontinuation, using the number of randomized subjects as denominator for the percentages.
- Number of days in the study among the randomized subjects, calculated as: End of Study Date (completion or discontinuation) – IP administration date + 1.

The following termination reasons as recorded on the End of Study form will be considered:

- Adverse event
- Death
- Lost to follow-up
- Physician decision
- Study terminated by sponsor
- Subject non-compliance/protocol violation
- Withdrawal of consent

A listing will present subject enrollment, with the protocol version for which subject was enrolled, and the inclusion in each analysis population.

A separate listing by subject will display the details of screen failure reason of each subject.

A by-subject listing will display subject disposition. All randomized subjects will be included.

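### The Safety, DLAE and PD analysis sets require randomization, so the never-randomized sentinel subjects fall out of the main safety tables

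*SAP*

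**What the plan says.** **Analysis sets.** SAP V.K gives: "Safety Evaluation Population: subjects who are randomized and have a dose of IP (either JK07 or placebo) administered". The Safety row of Protocol Table 11 has the same condition, "All subjects randomly assigned to the IP and who take at least 1 dose of IP", and so does the synopsis. In the SAP the DLAE set is "all subjects in the safety population who have a dose of IP (either JK07 or placebo) administered", with 15-day follow-up completed, so it inherits the condition. For the PD/biomarker set the SAP states: "The PD population will include all randomized subjects who have a dose of IP (either JK07 or placebo) administered". The PK set carries no such requirement: "PK Evaluation Population: subjects who have a dose of IP (either JK07 or placebo) administered".

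**Sentinels.** Protocol 6.3 states: "All subjects other than sentinel subjects will be centrally assigned to randomized study treatment". SAP IV.D says the same, gives randomization numbers only to non-sentinels, and adds: "After a sentinel patient is enrolled, each cohort will randomize 4 subjects in a 3:1 ratio to JK07 vs. Placebo". The deviations listing in SAP VI.C treats sentinel and randomized as two separate categories.

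**Where the sets are used.** SAP VII runs all safety analyses on the Safety set and DLAE-specific analyses on the DLAE set. Demographics (SAP VI.A) cover randomized subjects. The disposition table (SAP VI.B) starts from everyone screened, but reports: "Number and percentage of subjects in each analysis population, using the number of randomized subjects as denominator". Days on study and the disposition listing are also limited to randomized subjects.

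**Precedence.** SAP I.B states that the SAP overrides the Protocol.

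**The concern.** Safety and tolerability is the primary objective. The sentinel is the first person exposed at each new dose, and is there so that a serious reaction can be found before the rest of the cohort is dosed. A safety set that leaves these subjects out discards some of the most informative exposures in the trial.

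The worst case is a dose level that the Data Review Committee closes after the sentinel alone. One person would have received JK07 and might have had the event that decided the matter, yet the adverse-event, laboratory, ECG and DLAE summaries would show nobody treated at that dose.

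The sets would also disagree with one another, because the PK set keeps the sentinels and the Safety set does not. Protocol 9.4.2 runs the concentration-QT analysis on the PD set, so the sentinels' paired ECG and concentration data would be lost there as well.

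**Working it through.** **1. Does the maximum sample size count sentinels?** A full cohort is 1 sentinel + 6 JK07 + 2 placebo = 9, and at most 7 cohorts are allowed (SAP IV.A).

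- With sentinels: 7 × 9 = 63, which matches the stated maximum.
- Randomized subjects only: 7 × 8 = 56, which does not.

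So the 63 includes 7 subjects who are never randomized.

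**2. JK07 exposures lost.** The base cohort is 1 sentinel + 3 JK07 + 1 placebo (SAP IV.D).

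| Design | JK07 dosed | JK07 in Safety set as written | Lost | Safety N, all dosed | Safety N as written |
|---|---|---|---|---|---|
| 5 cohorts of 5 | 5 × (1+3) = 20 | 5 × 3 = 15 | 5/20 = 25.0% | 25 | 20 |
| 7 cohorts of 9 | 7 × (1+6) = 49 | 7 × 6 = 42 | 7/49 = 14.3% | 63 | 56 |

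Placebo counts (5 and 14) do not change. The whole loss falls on the active arm.

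**3. Effect at one dose level.** If only the sentinel of a base cohort has a DLAE, the reported rate changes from 1/4 (25%) to 0/3 (0%).

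**4. What a clean dose level could rule out.** With zero events in *n* subjects, the one-sided 95% upper bound on the event rate is 1 − 0.05^(1/*n*).

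- Base cohort: 1 − 0.05^(1/3) = 63.2%, against 1 − 0.05^(1/4) = 52.7% with the sentinel.
- Expanded cohort: 39.3% (*n* = 6), against 34.8% (*n* = 7).

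**5. Chance of seeing at least one event.** This is 1 − (1 − *p*)^*n*. The documents give no event rate, so *p* is an assumption.

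| Assumed *p* | *n* = 3 | *n* = 4 | *n* = 6 | *n* = 7 |
|---|---|---|---|---|
| 5% | 14.3% | 18.5% | 26.5% | 30.2% |
| 10% | 27.1% | 34.4% | 46.9% | 52.2% |
| 30% | 65.7% | 76.0% | 88.2% | 91.8% |

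**6. Disposition percentages.** If every JK07 subject qualifies for the PK set and the table is shown by dose, the PK percentage over randomized subjects is 4/3 = 133% in a base cohort and 7/6 = 117% in an expanded one. A percentage above 100 shows that the numerator and denominator come from different groups.

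**7. Protocol against SAP.** Protocol Table 11 requires randomization only for the Safety set. Its DLAE and PD rows ask only for dosing plus follow-up or a post-dose measurement. The SAP adds the randomization condition to both. Its section on changes from the Protocol mentions only abnormal vital signs, so this narrowing is undeclared.

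**The case against.** The strongest reply is that this is loose drafting and not a decision to discard sentinels. The Protocol says that up to 63 subjects will be randomized, a figure reached only by counting sentinels, so its authors evidently used the word for everyone in a cohort. The SAP's deviations listing expects sentinels to appear. This is a fair reading of intent, but it does not rescue the text. The SAP describes the same 63 as enrolled, so it had the inclusive word available, and it still required randomization in V.K. The operative randomization rules in both documents put sentinels outside.

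Several limits do stand:

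- Subject protection is not affected. The Data Review Committee reviews each sentinel's safety data directly (Protocol 4.5 and 9.6).
- The clear loss is in summary tables. By-subject adverse-event listings are planned, although whether they too are confined to the Safety set depends on how SAP VII is read.
- Immunogenicity (SAP XI) names no analysis population, so the exclusion cannot be assumed there.
- The disposition table does count all screened subjects. Only its percentages, days on study and listing are restricted.
- A cohort de-escalated to a dose not above the highest confirmed safe dose needs no sentinel and loses nobody.
- The analyses are descriptive, and upper bounds on event rates are not planned outputs. Steps 4 and 5 of the check only illustrate what the smaller *n* costs.

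**Conclusion.** The concern holds. Applied literally, the SAP removes one JK07 subject per sentinel cohort from the Safety, DLAE and PD sets: a quarter of active subjects in a base cohort and a seventh in an expanded one, or 5 of 20 over the planned design and 7 of 49 at the maximum. These counts follow directly from the cohort structure and need no assumption beyond one dosed sentinel per cohort. The detection probabilities rest on assumed event rates, and the percentages above 100 on full PK evaluability.

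The Safety defect is in both documents. The DLAE and PD defects are in the SAP only, but the SAP prevails. Because the affected set carries the primary objective and the denominators would be wrong, this must be corrected before database lock, even though the exclusion was probably not intended.

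**What to change.** - **SAP V.K:** define the Safety set as all enrolled subjects, sentinel or randomized, to whom IP was administered, analyzed by treatment received. The DLAE set then follows. Remove the randomization condition from the PD set.
- **SAP VI.A and VI.B:** use enrolled subjects (sentinel plus randomized) for demographics, disposition percentages, days on study and the disposition listing.
- **SAP, changes from Protocol:** declare the revised Safety definition. Once the condition is removed, the DLAE and PD sets agree with the Protocol on this point.
- **Protocol:** change the Safety row of Table 11 and the matching synopsis entry at the next amendment. The DLAE and PD rows need no change.
- **Presentation:** flag sentinels as open-label in tables and listings. If an inferential comparison of JK07 with placebo is made, add a sensitivity analysis in randomized subjects only, since sentinels are neither blinded nor randomly allocated.

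The cost is wording and small programming changes, with no new data. SAP I.B allows modification until database lock; a later change would have to be reported as a deviation in the study report.
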